### 3.4 Outcomes

#### *Primary outcome*

Participants' engagement with the SHAPES app during the pilot as defined by the number of times the app is opened per day over three months.

#### *Secondary outcomes*

- Participants' user experience with the SHAPES app as measured using the User Experience Questionnaire –short version (UEQ-S)
- Usability of the SHAPES app as measured using the System Usability Scale
- Number and rate of successful registrations of each clinical parameter per participant, per day (heart rate, blood pressure, weight, oxygen saturation, blood glucose)
- Number and rate of control limits (upper and lower) successfully generated by the 'Vitals Control' analytic tool per person (rate defined as number of pairs of limits generated per week during the pilot)

- Number and rate of heart failure decompensation prediction (HFPred) risk scores successfully generated per person (rate defined as number of scores generated per week during the pilot)
- Change in hospitalisation rate per person (hospitalisations/month) and A&E attendance rate (attendance/month) three months prior to baseline compared with 3 months during the pilot
- Participants' self-reported medication adherence as measured using the Medication Adherence Report Scale (MARS) at baseline and at the end of the pilot
- Participants' beliefs about medicines as measured using the Beliefs about Medicines Questionnaire (BMQ) at baseline and at the end of the pilot
- Correlation between participants' self-reported medication adherence and beliefs about medicines
- Number and rate (score/week) of heart failure decompensation prediction (HFPred) risk scores successfully generated per person during the pilot
- Correlation between HFPred scores and unscheduled care during the pilot (unscheduled care defined as composite of hospitalisations, A&E attendances, specialist contacts, out-of-hours contacts)
- Health-related quality of life as measured using the EQ-5D-5L questionnaire (ref) at baseline and at the end of the pilot
- Exploration of healthcare practitioners' views on integration and alignment of the SHAPES platform and Digital Solutions with current care pathways
- Exploration of healthcare practitioners' views about their trust and acceptance of the SHAPES platform and Digital Solutions
- Exploration of participants' views about their trust and acceptance of the SHAPES app.
- Exploration of user engagement behaviors

#### *Tertiary outcomes*

The following outcomes align with the general purposes of the SHAPES large-scale piloting campaign and data will be harmonised with outcome data from all pilots in the campaign:

- Participants' self-efficacy as measured using the general self-efficacy scale
- Participants' extent of social support as measured using the Oslo Social Support Scale (OSSS-3)
- Participants' health literacy as measured using the Single-item Health Literacy Measure (HLM1)
- Participation in society as measured using non-validated participation questions
- Participants' quality of life as measured using the WHOQOL-BREF
- Health-related quality of life as measured using the EQ-5D-5L
- Usability of the SHAPES app as measured using the System Usability Scale
- Technology Acceptance
- Exploration of participants' views about their trust and acceptance of the SHAPES platform and Digital Solutions
- Exploration of healthcare practitioners' views about their trust and acceptance of the SHAPES platform and Digital Solutions
- Change in health service utilisation for unscheduled care related to heart failure and diabetes as measured by:
  - Number of hospitalisations
  - A&E attendances
  - Out of hours contacts
  - Contacts with specialist services

- Economic impact of the intervention as measured by comparing the cost of the intervention (devices, SHAPES platform and digital solutions; staffing) versus the cost of unscheduled care related to heart failure and diabetes during the pilot.

*Table 1: Table of outcomes mapped to objectives of pilot*

| Objective  | Outcome measure   | Timepoint(s) of evaluation of outcome measure (if applicable)                              |
|--|---|--|
| To investigate user engagement with the SHAPES app and Digital Solutions   | Participants' engagement with the SHAPES app during the pilot as defined by the number of times the app is opened per day per person over three months.   | End of pilot   |
|  | User experience as measured using the user experience questionnaire –short version (UEQ-S)  | End of pilot   |
|  | System Usability Score  | End of pilot   |
| To validate the capability of the SHAPES platform and Digital Solutions to implement a personalised approach to achieve safe and effective use of medicines in homes.                         | Number and rate of successful registrations of each clinical parameter per participant, per day (heart rate, blood pressure, weight, oxygen saturation, blood glucose)                                      | End of pilot   |
|  | Number and rate of control limits (upper and lower) successfully generated by the 'Vitals Control' analytic tool per person (rate defined as number of pairs of limits generated per week during the pilot) | End of pilot   |
|  | Number and rate of heart failure decompensation prediction (HFPred) risk scores successfully generated per person (rate defined as number of scores generated per week during the pilot)                    | End of pilot   |
|  | Number and rate of views of medication list (rate as defined as number of views per week during the pilot)  | End of pilot   |
| To validate the capability of the SHAPES platform and Digital Solutions to achieve better patient outcomes by initiating, developing and sharing best practice with regards to medicines use. | Change in use of unscheduled care related to heart failure and diabetes as measured by: 
 
• Rate of hospitalisation
 
• Rate of A&E attendance
 
   | 3 months prior to baseline and end of pilot
3 months prior to baseline and end of pilot |

|  |   |                           |
|--|---|---------------------------|
| To validate the capability of the SHAPES platform and Digital Solutions to address and improve deficiencies with adherence to medicines and treatments.                            | Medication Adherence Report Scale (MARS)  | Baseline and end of pilot |
|  | Beliefs about Medicine Questionnaire (BMQ)  | Baseline and end of pilot |
|  | Correlation between participants' self-reported medication adherence and beliefs about medicines  | After pilot               |
| To validate the capability of the SHAPES platform and Digital Solutions to improve data collection to develop predictive algorithms for heart failure decompensation.              | Number and rate of heart failure decompensation prediction (HFPred) risk scores successfully generated with complete data collection per person (rate defined as number of scores generated per week during the pilot)  | End of pilot              |
| To validate the capability of the SHAPES platform and Digital Solutions to identify associations between precursor signs of deterioration and unscheduled healthcare resource use. | Correlation between HFPred scores and unscheduled care during the pilot
Association between HFPred scores and unscheduled care during the pilot (unscheduled care defined as composite of hospitalisations, A&E attendances, specialist contacts, out-of-hours contacts) | After pilot               |
| To validate the capability of the SHAPES platform and Digital Solutions to improve older individuals' quality of life  | EQ-5D-5L  | Baseline and end of pilot |
| To explore the integration of the SHAPES platform and Digital Solutions to align with current and developing care pathways.  | Exploration of healthcare practitioners' views on integration and alignment of the SHAPES platform and Digital Solutions with current care pathways   | During or after pilot     |
| To explore user trust and acceptance of the SHAPES platform and Digital Solutions.   | Exploration of participants' views about their trust and acceptance of the SHAPES app.  | End of pilot              |
|  | Exploration of user engagement behaviors  | After pilot               |

|   |   |  |
|---|---|--|
| To validate the capability of the SHAPES Platform and Digital Solutions to support and extend healthy and independent living for older individuals who are facing permanently or temporarily reduced functionality and capabilities | General Self-Efficacy Scale   | Baseline; End of pilot; 3-month follow-up  |
|   | Oslo Social Support Scale (OSSS-3)  | Baseline; End of pilot; 3-month follow-up  |
|   | Health literacy as measured using the Single-item Health Literacy Measure (HLM1)  | Baseline; End of pilot; 3-month follow-up  |
|   | Participation measure (non-validated)   | Baseline; End of pilot; 3-month follow-up  |
| To validate the capability of the SHAPES Platform and Digital Solutions to improve the older individuals' health outcomes and quality of life   | WHOQOL-BREF   | Baseline; End of pilot; 3-month follow-up  |
|   | EQ-5D-5L  | Baseline; End of pilot; 3-month follow-up  |
| To validate the capability of the SHAPES Platform and Digital Solutions to gain the older individuals' trust and acceptance   | System Usability Score  | End of pilot   |
|   | Technology Acceptance measure (non-validated)   | End of pilot   |
| To validate the capability of the SHAPES Platform and Digital Solutions to gain the care professionals' trust and acceptance  | Exploration of healthcare practitioners' views on integration and alignment of the SHAPES platform and Digital Solutions with current care pathways   | After pilot  |
| To validate the capability of the SHAPES Platform and Digital Solutions to contribute for the reduction of the  | Change in health service utilisation for unscheduled care related to heart failure and diabetes as measured by: 
 
• Number of hospitalisations
 
• A&E attendances
 
 | 3 months prior to baseline and end of pilot
3 months prior to baseline and end of pilot |

|   |  |  |
|---|--|--|
| workload of medical professionals   | 
 
• Out of hours contacts
 
• Contacts with specialist services
 
   | 3 months prior to baseline and end of pilot
3 months prior to baseline and end of pilot |
| To validate the capability of the SHAPES Platform and Digital Solutions to deliver efficiency gains in health and care delivery across Europe | Economic impact of the intervention as measured by comparing the cost of the intervention (devices, SHAPES platform and digital solutions; staffing) versus the cost of unscheduled care related to heart failure and diabetes during the pilot. | After the pilot  |

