Participants will receive one-on-one, face-to-face introduction to the app and training on how to use both it and the connected medical devices. A user manual will contain detailed step-by-step supportive guidance and information, and will be provided to participants in hard-copy format for reference by participants during the pilot. There will be a run-in period of approximately one week wherein the participant can familiarise themselves with the app and liaise with the researchers to troubleshoot any problems they may be experiencing with the technology. Participants will be asked to use the app and connected devices for 12 weeks. Researchers will contact participants by telephone at the end of week 1, if there are three or more consecutive days where no data has been received (up to a maximum of four times during the pilot) and monthly (if required) thereafter. These telephone contacts are to enable the researchers to support participants with their use of the technology and troubleshoot any issues they may be experiencing (no health advice or clinical support will be provided by the researchers. If participants have any health concerns they will be encouraged to contact their specialist care team).

All data entered or transferred into the SHAPES app (i.e., clinical readings, survey responses) is pseudonymised and will be stored in the technical partners' (EDGE and GNOMON) servers and then uploaded to the SHAPES big data platform. Selected data is then processed by two further SHAPES digital solutions; a heart failure decompensation risk prediction algorithm (VICOM) and an analytic tool that generates personalised dynamic thresholds for participants' clinical parameters (TREE). These digital solutions have not yet been validated or CE-marked for use as medical devices. Therefore, the outputs will not be used to inform clinical care, but rather to determine whether the digital solutions are capable of producing outputs reliably using the available data, and to indicate if there are any associations between the risk scores generated and the participants' use of unscheduled care.

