### *Withdrawal of consent*

Participants can withdraw from the study at any point, no reason needs to be provided, however, the participant will be asked if they would like to state a reason for withdrawal.

Clarification will be sought as to whether the participant would like to withdraw all data or if data provided up to the point of withdrawal may be retained and used in the analysis and description of the pilot cohort.

The following details will be noted upon withdrawal of consent; date, reason (if provided), whether consent for a follow-up interview or consent to use data until date of withdrawal remains.

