##### *Service user baseline procedures*

- Questionnaires — Barthel Index, Gijon Scale, EHFS, MARS, BMQ, EQ-5D-5L, GSES, OSSS-3, HLM1, participation measure, WHOQOL-BREF
- Medical history data — height, weight, left ventricular ejection fraction, heart rhythm, implanted devices, medical conditions, heart failure stage, dyspnoea level, smoking status, leg pain symptom question
- Demographic data — including DOB, education, sex, marital status, occupational status, caregiver status, housing details
- Technical data — device monitoring details e.g. model, manufacturer, serial number and preferred time of day for reminders/questionnaires, make and model of the participants own smartphone/tablet
- Laboratory results — urea, creatinine, sodium, potassium, haemoglobin, cholesterol, eGFR, HbA1c, ACR, urine creatinine, urinary albumin-creatinine ratio
- Unscheduled care — hospitalisations (previous 3 months), and previous month hospital readmissions, A&E attendances, out of hours care, specialist service contacts, emergency ambulance call outs

- Current prescribed medication — name, frequency, strength, chronic or as required, stop date if stopped during the pilot, start date if started during the pilot.

*Service user study visits and procedures*

- During the pilot, the participant will be asked to record the following at least once daily, as appropriate, via the SHAPES app; blood pressure, heart rate, oxygen saturation, weight (which will include body mass index, body fat, visceral fat, skeletal muscle, basal metabolic rate).
- Participants diagnosed with diabetes and monitoring blood glucose regularly will be requested to record their blood glucose with the same frequency as directed by their doctor on the SHAPES app.
- Participants diagnosed with heart failure will be asked a series of daily questions about their heart failure symptoms administered via the SHAPES app.
- All participants will be asked about their adherence to medication with a weekly MARS questionnaire administered via the SHAPES app.
- During the pilot, the patient may view their medication list
- Unscheduled care updates — any updates to baseline hospitalisations, hospital readmissions, A&E attendances, out of hours care, specialist service contacts, emergency ambulance call outs recorded from medical notes
- Prescribed medication updates — any updates to prescribed medications notified by participant

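### The tertiary utilisation counts have no common observation time, so an apparent change in workload can arise from window length alone, in either direction

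*Protocol*

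**What the plan says.** The tertiary outcome in section 3.4 is "Change in health service utilisation for unscheduled care related to heart failure and diabetes as measured by" four components, the first written as "Number of hospitalisations". The other three (A&E, out-of-hours and specialist contacts) carry no unit, and no denominator is given for any of them. In Table 1 this outcome is the only measure for the objective of reducing professional workload, and each component is timed as "3 months prior to baseline and end of pilot".

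The same section treats two of these event types differently as a secondary outcome: "Change in hospitalisation rate per person (hospitalisations/month) and A&E attendance rate (attendance/month) three months prior to baseline compared with 3 months during the pilot". Table 1 likewise lists rates in that row.

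Four other places fix the observation time:

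- Section 3.3: "Participants will be asked to use the app and connected devices for 12 weeks". The timeline in section 3.5 agrees, running from T0 to T12.
- Sections 3.5 and 3.8.1 allow the end-of-pilot visit up to 14 days late. During the pilot, unscheduled care is taken from medical notes.
- The baseline data list in section 3.8.1 collects "hospitalisations (previous 3 months), and previous month hospital readmissions, A&E attendances, out of hours care, specialist service contacts, emergency ambulance call outs".
- Under withdrawal of consent in section 3.7, participants choose whether data up to that point are kept or all data are removed. Staff record "whether consent for a follow-up interview or consent to use data until date of withdrawal remains".

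**The concern.** A change in counts is interpretable only if both counts cover the same length of time, or are divided by it. Here the before and during windows differ in length, the two passages that define the before window disagree for three of the four components, and the date on which pilot counting stops is not fixed.

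The study is single-armed, so there is no control group in which the same artefact would show. A difference due only to calendar length could be reported as reduced workload for hospitalisations, or as sharply increased workload for A&E, out-of-hours and specialist contacts. The secondary A&E rate is affected too. It is defined over three months before baseline, while the data list appears to supply one.

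**Working it through.** The protocol gives no event rate, power figure or expected change, so there is no stated figure to reproduce. The check asks what each raw count comparison would show if nothing changed.

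**Inputs**
- Month: 365.25/12 = 30.44 days. Three months = 91.3 days (Table 1); actual calendar spans run from 89 to 92 days.
- Pilot: 12 weeks = 84 days (section 3.3), or up to 84 + 14 = 98 days if counting runs to a late closing visit (section 3.8.1).
- Baseline look-back as worded in section 3.8.1: 91.3 days for hospitalisations, 30.4 days for A&E, out-of-hours and specialist contacts.
- Withdrawal share d: not stated. Assumed 0 to 30%, spread evenly over the 84 days (mean 42 days observed), with data kept to withdrawal and full baseline counts kept.

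**Formula.** At a constant event rate, expected pilot count / expected baseline count = mean pilot days / baseline days, where mean pilot days = (1 − d) × T + d × 42 and T is 84 or 98.

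**No withdrawal**
- Hospitalisations, day-84 close: 84/91.3 = 0.92 (84/92 = 0.913 to 84/89 = 0.944), an apparent fall of about 8%.
- Hospitalisations, day-98 close: 98/91.3 = 1.07, an apparent rise.
- One-month components, day-84 close: 84/30.4 = 2.76, an apparent rise of 176%.

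**With assumed withdrawal**

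| d | Mean days (T = 84) | Ratio, 3-month look-back | Ratio, 1-month look-back | Ratio, 3-month look-back, T = 98 |
|---|---|---|---|---|
| 0 | 84.0 | 0.92 | 2.76 | 1.07 |
| 10% | 79.8 | 0.87 | 2.62 | 1.01 |
| 20% | 75.6 | 0.83 | 2.48 | 0.95 |
| 30% | 71.4 | 0.78 | 2.35 | 0.89 |

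With a day-98 close, the hospitalisation ratio stays above 1 until d = (98 − 91.3)/(98 − 42) = 0.12. For the one-month components, even if everyone who withdrew did so on day 0, a fall would need more than 1 − 30.4/84 = 64% of participants to leave.

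**In events.** Assume 0.1 events per person-month in 30 participants. Three months gives 30 × 0.1 × 3 = 9.0 events, 12 weeks gives 30 × 0.1 × 2.76 = 8.3, and one month gives 3.0.

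**Secondary rates.** Twelve weeks is 84/30.44 = 2.76 months. If pilot events are divided by a nominal 3 months, as "three months prior to baseline compared with 3 months during the pilot" invites, the pilot rate is understated by 1 − 2.76/3 = 8%. A monthly rate protects the comparison only if it is divided by the time actually observed.

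**After the fix.** With events divided by the person-time in which they were observed, the no-change ratio is 1.00 for every component, provided withdrawal is unrelated to event risk.

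**The case against.** Several points can fairly be made for the plan.

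- The outcome is tertiary, and monthly rates for hospitalisation and A&E already stand as secondary outcomes. In the illustration the 12-week shortfall is 0.7 of 9 events. The Poisson error of such a ratio is about √(1/9 + 1/8.3) = 0.48 on the log scale, far more than 8%. This limits the importance of the hospitalisation gap. It does not dispose of a 2.76-fold difference.
- The data list can be read so that the one-month limit covers readmissions only. The list would then give no look-back for the other contacts, and Table 1 alone would supply three months. That reading removes the 2.76 but leaves the 0.92 and an unclear data list.
- Handling of withdrawals belongs in the Data Analysis Plan, which is not shown. The paired tests in section 3.8.11 could be run on completers, which would remove the truncation. This stands. The outcome's metric and window, however, are set in the protocol itself.
- The tertiary items are to be harmonised across the campaign's pilots and analysed by its coordinators (section 3.8.10), so replacing the counts at one site could break that. This also stands, and it is a reason to keep counts alongside rates.

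A reader might go further and infer that unscheduled care will appear to fall whatever happens, and that withdrawal inflates the apparent benefit. The documents do not support this. The direction reverses for three of the four components on the natural reading of the data list, and for hospitalisations if counting runs to a late visit. No withdrawal rate is given, participants may remove all their data (both windows then vanish), and nothing says that partial pilot counts will be compared with full baseline counts.

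**Conclusion.** The point holds as a defect of measurement with no fixed direction. Followed as written, the tertiary comparison has a no-change ratio of about 0.92 for hospitalisations with counting to day 84, 1.07 with counting to day 98, and about 2.76 for any component with a one-month look-back. None of these is 1.00.

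The figures assume a constant event rate. The 2.76 also assumes that the one-month limit applies to A&E, out-of-hours and specialist contacts, which is how the list reads. The effect of withdrawal is to lower the ratios if truncated counts are used. Its size is unknown, and the tabulated values only illustrate it.

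The larger problem is the conflict between Table 1 and the baseline data list, which also reaches the secondary A&E rate. The 8% gap alone would be minor in 30 participants. The change is worth making before analysis because it is cheap and a single-arm study cannot reveal the artefact afterwards.

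**What to change.** 1. Reconcile the baseline data list in section 3.8.1 with Table 1, so that every utilisation component has the same stated look-back.
2. Make the before window equal in length to the pilot window, for example the 84 days ending the day before baseline and days 0 to 83 of the pilot. Fix both by date, independently of when the closing visit takes place.
3. In the tertiary outcome and the workload row of Table 1, analyse change as events per person-time observed, truncated at withdrawal. Apply the same windows and denominators to the secondary hospitalisation and A&E rates, so that 12 weeks is not divided as three months.
4. Keep the raw counts as descriptive results and for campaign harmonisation, each reported with its observation time.

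Cost: wording in sections 3.4 and 3.8.1 and in Table 1. If only one month would otherwise be collected for A&E, out-of-hours and specialist contacts, a longer look-back in the medical notes is needed, so some extra data collection cannot be ruled out. Moving from three months to 84 days drops about one week (91.3 − 84 = 7.3 days) of baseline hospitalisations from the comparison.

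### The economic-impact outcome has no cost without the intervention, so it cannot show the efficiency gain it is meant to measure

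*Protocol*

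**What the plan says.** The last tertiary outcome in Protocol section 3.4 reads "Economic impact of the intervention as measured by comparing the cost of the intervention" (devices, platform and digital solutions, staffing) "versus the cost of unscheduled care related to heart failure and diabetes during the pilot". Table 1 repeats this wording, sets the evaluation after the pilot, and makes it the only measure for the objective to "deliver efficiency gains in health and care delivery across Europe".

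The neighbouring outcome is built differently. Change in use of unscheduled care (hospitalisations, A&E attendances, out-of-hours contacts, specialist contacts) is timed in Table 1 at "3 months prior to baseline and end of pilot". The related secondary outcome compares monthly rates of hospitalisation and A&E attendance "three months prior to baseline compared with 3 months during the pilot". These outcomes are counts or rates, they are mapped to other objectives (better patient outcomes and workload), and nothing says they will be costed.

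Section 2.4 describes a non-randomised, single-arm study that aims to recruit 30 service users.

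**The concern.** An efficiency gain is a statement about total cost with the intervention against total cost without it. The outcome sets two costs side by side that both belong to the period with the intervention. There is no control arm to supply the missing cost, and the definition does not use the period before baseline.

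Carried out exactly as written, the analysis gives two totals and no statement about gain or loss. Section 3.8.10 says that the primary, secondary and selected tertiary measures will be analysed to judge whether the pilot met its objectives, and section 4.9 makes the final report public. A cost pair that cannot be interpreted could be read there as evidence for or against efficiency.

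**Working it through.** **Inputs.** The protocol gives no costs, so all cost figures below are assumed, per participant, and only show how the comparison behaves.

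- C = cost of the intervention (section 3.4)
- U1 = cost of unscheduled care during the pilot (section 3.4)
- U0 = cost of unscheduled care over an equal period without the intervention (not in the outcome)

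**Formulas.**

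- Comparison as written: C against U1.
- Net cost: N = C + U1 − U0. A gain means N < 0, that is, U0 > C + U1.

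**Check 1: does the written comparison respond to U0?** Take C = 1,000 and U1 = 1,500.

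| U0 | As written (C, U1) | N = C + U1 − U0 |
|---|---|---|
| 3,000 | 1,000, 1,500 | −500 (saving) |
| 1,500 | 1,000, 1,500 | +1,000 |
| 500 | 1,000, 1,500 | +2,000 |

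Break-even is at U0 = 1,000 + 1,500 = 2,500. The written result is identical in all three rows, so it cannot say on which side of break-even the pilot falls.

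**Check 2: does the written comparison at least move the right way?** Hold U0 = 3,000 and C = 1,000, and let care during the pilot become cheaper.

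| U1 | C/U1 | N |
|---|---|---|
| 2,500 | 1,000/2,500 = 0.40 | 1,000 + 2,500 − 3,000 = +500 |
| 500 | 1,000/500 = 2.0 | 1,000 + 500 − 3,000 = −1,500 |

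Net cost improves by 2,000, while the intervention goes from 0.40 to 2.0 times the cost of unscheduled care. The more successful scenario looks relatively dearer. The algebra does not depend on the figures chosen.

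**Check 3: can U0 be formed from what is planned?** Largely yes, with one point to settle. Table 1 asks for three months before baseline for all four components. The baseline procedures in section 3.8.1 instead list "hospitalisations (previous 3 months), and previous month hospital readmissions, A&E attendances, out of hours care, specialist service contacts". This can be read as one month for everything except hospitalisations, or as one month for readmissions alone.

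- On the first reading, the look-back for A&E, out-of-hours and specialist contacts is 365.25/12 = 30.4 days, against a pilot of 12 × 7 = 84 days: 30.4/84 = 36%. If care were counted to the end of the +14-day visit window (98 days), it would be 30.4/98 = 31%.
- On the second reading there is no such shortfall.
- Even three full months (3 × 30.4 = 91 days) is not 84 days, so some scaling is needed in any case.

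This third check bears only on the repair. The defect shown in checks 1 and 2 does not depend on it.

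**The case against.** The strongest reply is that the protocol is not the whole plan. Section 3.8.10 refers to a Data Analysis Plan, which was not available here, passes harmonised tertiary data to the campaign coordinators, and adds an evaluation under the MAST framework that covers economic issues. The objective belongs to the whole campaign ("data will be harmonised with outcome data from all pilots in the campaign"), so 30 people at one trust were never going to settle it. The inputs for a pre-pilot cost sit one bullet above. A net-cost figure has problems of its own: recruitment draws partly on in-patient lists (section 3.7), so care use before baseline may be unusually high and the estimate would lean towards apparent savings. The intervention cost per participant also depends on how shared platform costs are allocated and how devices generally recovered at the end (section 4.8) are valued.

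Part of this stands. The outcome is tertiary, no decision rule hangs on it, and a before-after net cost would be descriptive, not causal. It does not rescue the definition, however. The protocol does not leave the comparator open; it fixes one, identically in two places, and that one cannot answer the objective. The MAST reference defines no cost comparison. Harmonising the same pair across pilots does not add the missing term if each pilot reports it as defined here.

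**Conclusion.** The concern holds. As worded, the economic-impact outcome cannot show an efficiency gain or loss, and it is the only measure mapped to that objective. In the illustration one and the same reported result is compatible with anything from a saving of 500 to a net cost of 2,000 per participant. Those amounts are assumed; the conclusion rests only on the absence of U0 from the definition and on the single-arm design.

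The consequence is limited to one tertiary outcome. It should be corrected because the correction is cheap and the result is to be published, but it does not threaten the pilot's main conclusions. A later analysis plan could add a comparator, but the protocol text would still need to agree with it.

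**What to change.** Either of two changes to section 3.4 and Table 1 would do.

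**Net-cost option.** Define net cost per participant as the intervention cost plus the difference between unscheduled-care cost during the pilot and before baseline, both scaled to the same number of days. The protocol already uses monthly rates for hospitalisation and A&E, so the scaling follows its own convention. State how intervention cost is allocated per participant. Report the result descriptively with an interval, labelled an uncontrolled before-after estimate open to regression to the mean. As a condition, reconcile the look-back wording in section 3.8.1 with the three months in the secondary outcomes and Table 1. Because tertiary data are harmonised across pilots, adding this measure beside the existing pair is easier than replacing it, which may need agreement beyond this site.

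**Relabel option.** Call the existing measure a descriptive cost report and state that no efficiency conclusion will be drawn from it.

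**Cost.** Relabelling takes one sentence and one table cell. The net-cost option takes one outcome line in two places, a clarified look-back, and the pilot-period unit costs applied to pre-baseline counts that Table 1 already requires. During-pilot updates, including "emergency ambulance call outs recorded from medical notes", come from a source that may also cover the longer look-back; the protocol does not say so for the baseline item, so this needs checking. With 30 participants the interval will be wide.
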